### 1.1 Study design

[figure not shown]
This study uses a randomized, double-blind, double-dummy, parallel-group design to assess the efficacy and safety of QMF149 150/80 microgram o.d. delivered via Concept1 compared with MF 200 microgram o.d. delivered via Twisthaler® in adult and adolescent patients with mild asthma (figure 1)

Approximately 750 patients (including approximately 50 adolescent patients) will be randomized into the two treatment groups with a randomization ratio of 1:1 (i.e. approximately 375 patients per treatment group). At least 676 randomized patients (338 per treatment group) are needed to complete the study treatment. Detailed information regarding sample size calculation is provided in [section 3](#).

This study will enroll multi-nationally and patients will be stratified according to prognostic factors of age (12 to 17 years or  $\geq 18$ ) and non-prognostic factor region to achieve improved homogeneity within each stratum.

No interim analysis for efficacy is planned. It is planned that the independent Data Monitoring Committee (DMC) will review semi-blinded (i.e., treatment groups names as T01 and T02) safety data (as described in Section 8.4 of the protocol). The details of the information flow, confidentiality and specific analysis will be available from the DMC Charter.

**Figure 1 Study design**

## 1.2 Study objectives and endpoints

Section 2 of the study protocol lists the following primary, key secondary, other secondary ██████████ objectives.

### 1.2.1 Primary objective

The primary objective of this study is to demonstrate the superiority of QMF149 150/80 microgram o.d. (in the evening) delivered via Concept1 compared with MF 200 microgram o.d. (in the evening) delivered via Twisthaler® in terms of trough FEV1 after 12 weeks of treatment in adults and adolescents.

### 1.2.2 Key secondary objective

The key secondary objective is to demonstrate the superiority of QMF149 150/80 microgram to MF 200 microgram o.d. in terms of ACQ-7 after 12 weeks of treatment.

### 1.2.3 Other secondary objectives

Other secondary objectives will evaluate the efficacy of QMF149 150/80 microgram versus MF 200 microgram o.d. in terms of:

#### Lung function:

- Trough FEV1 at Day 2 of treatment period (defined as the mean of 23 h15 min and 23 h 45min FEV1 values post dose of Day 1.)
- Pre-dose FEV1 (defined as the mean of -45 min and -15 min FEV1 values pre-evening dose) at 4 weeks
- Forced Vital Capacity (FVC) and Forced Expiratory Flow between 25% and 75% of FVC (FEF25-75) over 12 weeks
- Morning and Evening Peak Expiratory Flow Rate (PEF) over 4 and 12 weeks of treatment.

#### Symptoms and asthma control:

- Percent of patients achieving the minimal important difference (MID) in ACQ-7 (i.e. at least 0.5 decrease from baseline) at Week 12
- Percentage of asthma symptoms free days, the percentage of nights without nighttime awakenings, and the percentage of mornings without symptoms on awakening as recorded by daily electronic Diary (e-Diary) over 12 weeks of treatment
- Asthma control as assessed by the Asthma Control Questionnaire (ACQ-7) at Week 4
- Rescue salbutamol/albuterol usage (mean daily, nighttime and daytime use) from e-Diary recordings over 12 weeks of treatment
- Percentage of rescue medication free days over 12 weeks of treatment period.

#### Exacerbations:

- To evaluate the efficacy in terms of asthma exacerbation-related parameters described below during 12 weeks of treatment. The analysis will be performed by exacerbation category wherever specified. The exacerbation categories are: All (mild, moderate, severe) and the combination of moderate or severe:
  - Time to first asthma exacerbation by exacerbation category.
  - Annual rate of asthma exacerbations by exacerbation category.
- Quality of life as assessed by Asthma Quality of Life Questionnaire (AQLQ) over 12 weeks of treatment period.

The following safety and tolerability endpoints will be evaluated:

- Cumulative incidence of the composite endpoint of serious asthma outcomes (i.e. asthma-related hospitalization, asthma-related intubation, or asthma-related death) over 12 weeks of treatment.
- AEs, vital signs, electrocardiogram (ECG), and laboratory analysis (hematology, blood chemistry including glucose and potassium, urinalysis, evening plasma cortisol) over 12 weeks of treatment.

## 2 Statistical methods

### 2.1 Data analysis general information

The final analysis will be performed by [REDACTED]. The most recent version of SAS available in the statistical programming environment of [REDACTED] will be used for the analysis.

#### 2.1.1 General definitions

The terms ‘study treatment’ which has been used in this document actually refer to ‘double-blind treatment’.

##### 2.1.1.1 Study day

Study day will be defined as the number of days since the date of first dose of study treatment. The date of first dose of study treatment will be defined as Day 1 and the day before the first dose of study treatment will be defined as Day -1.

Therefore, for a particular date, study day will be calculated as follows:

- for dates on or after the first date of study treatment,  
Study day = Assessment date – Date of first dose of study treatment + 1;
- for dates prior to the first date of study treatment,  
Study day = Assessment date – Date of first dose of study treatment.

If a patient has no study treatment, the randomized date will be used instead of the date of first dose of study treatment. Then, the randomized date is defined as Day 1 and the day before the randomization was defined as Day -1.

### 2.1.1.2 Baseline definition

In general, baseline is defined as the last measurement before the first dose of study treatment at the evening of Day 1.

Parameter	Baseline assessment	Detail
Post-dose FEV 1 , Pre-dose trough FEV 1 , Trough FEV 1	45 min and 15 min pre-dose FEV 1 at Day 1	The average of the values taken at -45 and -15 min
Post-dose FVC, Pre-dose trough FVC, Trough FVC	45 min and 15 min pre-dose FVC at Day 1	The average of the values taken at -45 and -15 min
Post-dose FEF 25-75 , Pre-dose trough FEF 25-75 , Trough FEF 25-75	45 min and 15 min pre-dose FEF 25-75 at Day 1	The average of the values taken at -45 and -15 min
ACQ-7	Prior to first dose of study treatment at Day 1	The average of responses of 7 questions
ACQ-5	Prior to first dose of study treatment at Day 1	The average of responses of first 5 questions
Diary data (PEF, symptoms, and rescue medication use)	Last 21 days of run-in period between run-in Visit 101 and up to one day before first dose of study treatment	The average from all non- missing records or percentage of days free of symptoms or rescue medication use
Laboratory data (hematology, biochemistry, urinalysis, and plasma cortisol)	20 min pre-dose at Day 1	
Vital signs (pulse rate and systolic and diastolic blood pressures)	25 min pre-dose at Day 1	
Height and weight	Run-in Visit 101	
ECG	35 min pre-dose at Day 1	

Detail descriptions for calculating baseline values are provided in the latter sections.

### 2.1.1.3 Post-baseline measurement

Post-baseline measurements are defined as those assessments after the first dose of study treatment.

When change from baseline is of interest the following formula will be used for each scheduled visit and time-point where baseline and post-baseline values are both available:

Change from baseline = post-baseline value – baseline value.

Detail descriptions for calculating post-baseline values are provided in the latter sections.

## 2.2 Analysis sets

The following analysis sets are defined:

- The randomized (RAN) set will consist of all patients who were assigned a randomization number, regardless of whether or not they actually received study treatment. Patients in RAN will be analyzed according to the treatment they were randomized to. The RAN set will be used for a summary of patient disposition, demographics and baseline characteristics.
- The Full Analysis Set (FAS) will consist of all patients in the RAN set who received at least one dose of study treatment. Following the intent-to-treat principle, patients will be analyzed according to the treatment they were assigned to at randomization. The FAS will be used in the analysis of all efficacy variables.
- The Per-Protocol set (PPS) will include all patients in the FAS who did not have any major protocol deviations. The list of major protocol deviations will be available in [Appendix 6.7](#) prior database lock. Patients will be analyzed according to the treatment they received. The PPS will be used for supportive analysis of the primary analysis only.
- The Safety Set will consist of all patients who received at least one dose of study treatment including non-randomized patients who received study treatment in error. Patients will be analyzed according to the treatment they received. If patients switch double-blind treatment during the study, they will be counted and analyzed only once according to their initial treatment. The safety set will be used in the analysis of all safety variables.

•

### 2.2.1 Subgroup of interest

Subgroup analyses of primary, key and other secondary, [REDACTED] objectives will be performed for adolescent patients (12 - 17 years old). These analyses will be identified in the TFL shells. For tables presenting results from statistical models, the treatment effects in adolescent patients will be derived from the treatment x age subgroup interaction term by including all patients in the analysis.

At week 12, the following subgroups will be used for supporting analyses of primary endpoint trough FEV1:

- Age group (12 to 17 years,  $\geq 18$  years)
- Race (Caucasian, Asian, Black and other)
- Gender (male, female)

- History of asthma exacerbation in the 12 months prior to Screening (Yes, No)
- Patients' prior therapies before Run-in period (eg. low dose ICS without LABA, low dose ICS with LABA)
- FEV1 response according to % predicted FEV1 range at Baseline (60 %-< 70%, 70% to < 90%)
- ACQ-7 Baseline (1.5- < 2, 2-< 2.5,  $\geq 2.5$ )

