## 2.5.2 Statistical hypothesis, model, and method of analysis

The comparison of QMF149 150/80 microgram versus MF 200 microgram will be evaluated by testing the following null hypothesis (H0) versus the alternative hypothesis (Ha):

H0: QMF149 treatment group is equal to MF treatment group in trough FEV1 at Week 12

Ha: QMF149 treatment group is not equal to MF treatment group in trough FEV1 at Week 12

The primary variable will be analyzed using a mixed model for repeated measure (MMRM) on the FAS. The model will contain treatment, age (12 to 17 or ≥ 18 years), region, visit (Days 2 and 85), and treatment-by-visit interaction as fixed effects with baseline FEV1 measurement, baseline-by-visit interaction, FEV1 prior to inhalation and FEV1 within 15 to 30 min post inhalation of salbutamol/albuterol (components of SABA reversibility) as covariates, and center nested within region as a random effect. The within-patient correlation will be modeled using an unstructured covariance matrix in the mixed model. The Kenward-Roger approximation will be used to estimate denominator degrees of freedom ([Kenward and Roger, 1997](#)). If the model does not converge, with unstructured covariance matrix, the compound symmetry covariance matrix will be used in the mixed model, if the model still does not converge the random effect will be removed, if the model converges after removing the random center effects, the original model without random center effects will be re-assessed. The restricted maximum likelihood method will be used. The between-treatment comparison will be carried out using the adjusted mean (least-squares mean (LS mean)) difference based on the treatment main effect and the coefficient for the treatment-by-visit interaction for Day 85 and treatment.

The estimated adjusted treatment difference (QMF149 – MF) will be displayed along with the associated standard error, 2-sided 95% confidence interval (CI), and p-value (2-sided).

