#### **2.5.4 Supportive and Sensitivity analyses**

As supportive analysis, the same MMRM used in the primary analysis will be also performed on the PPS to assess the treatment effect in protocol adherers.

In addition, the same primary MMRM on the FAS will be performed including all spirometric measures irrespective of systemic corticosteroid or rescue medication use but those measures taken outside of the 22 – 25 hour post-evening dose time window will not be included.

As a sensitivity analysis, a so-called 'tipping point analysis' will be performed for the primary endpoint to evaluate the impact of a deviation from the MAR assumption of missing data. The delta-adjusting approach described in Ratitch et al (2013) will be used to find the tipping point, in a spectrum of conservative missing not at random (MNAR) assumptions, at which conclusions change from being favorable to QMF149 to being unfavorable. After such a tipping point is determined, clinical judgment can be applied as to the plausibility of the assumptions underlying this tipping point. This methodology would provide a good picture of what it would take to overturn study conclusions on the basis of varying assumptions about missing data. The basic idea is to first impute the missing values using a regression based multiple imputation (MI) method based on the MAR assumption. The imputed Week 12 values for the QMF149 arms are then adjusted by a delta value. A detailed description of the analysis steps are provided in [Section 6.6](#).

The exploratory subgroup analyses for trough FEV1 using MMRM will be performed (using the appropriate interaction term in the model and additional covariate as a fixed effect, if necessary) for the FAS population to explore the treatment effect in key demographic and disease related subgroups (See [Section 2.2.1](#) for the details of subgroups).

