## 2.6 Analysis of the key secondary objective

### 2.6.1 Key secondary endpoint

The key secondary objective is to demonstrate the superiority of QMF149 150/80 µg to MF 200 µg in terms of ACQ-7 after 12 weeks of treatment.

The ACQ-7 measures asthma symptom control and consists of seven items: five on symptom assessment, one on rescue bronchodilator use and one on airway calibre (FEV1 % predicted). Patient recall is one week. All 7 questions of the ACQ-7 are equally weighted. Items 1-5 are scored along a 7-point response scale, where 0 = good controlled and 6 = poor controlled. Item 6 is scored between 0 = no rescue medication and 6 = More than 16 puffs/inhalations most days. The 7th item will be scored by the investigator based on the FEV1 % predicted from the masterscope at the site (i.e., Score = 0 means > 95% of predicted FEV1, 1 = 90 – 95%, 2 = 80 – 89%, 3 = 70 – 79%, 4 = 60 – 69%, 5 = 50 – 59%, and Score = 6 means < 50% of predicted FEV1). The total score is calculated as the mean of all questions. The mean will be calculated as the sum of scores divided by the number of questions that were answered, as long as there were at least 6 questions answered and the missing question is neither Question 1 ('On average, during the past week, how often were you woken by your asthma during the night?') nor Question 7. In case of one missing response (not Question 1 or Question 7), first that missing response will be imputed as per the method given in [Section 2.6.3](#) and then the ACQ score will be calculated.

ACQ-7 measurements are scheduled for Days -21, 1, 30 and 84.

For the ACQ-7 score, the baseline value is defined as the score obtained at Day 1 prior to first dose of study treatment. If the value is missing, the last measurements from run-in visit 101 or unscheduled run-in visits will be used.

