## 6.6 Statistical methodology and assumptions

SAS codes for all statistical methodology described in this section will be included as programming note in TFL Shells.

- **Mixed Model Repeated Measures (MMRM)**

The following MMRM ANCOVA will be used for trough FEV1, ACQ-7, and other data:

Dependent variable = intercept + treatment + age group + region + baseline value + FEV1 prior to inhalation + FEV1 within 15 to 30 min post inhalation + visit + treatment\*visit + baseline value\*visit + random effect of center nested within region + error.

The within-patient correlation will be modeled using an unstructured covariance matrix in the mixed model. The Kenward-Roger approximation will be used to estimate denominator degrees of freedom (Kenward and Roger, 1997).

For the final analysis, if the model does not converge with unstructured covariance matrix, the compound symmetry covariance structure will be used, if the model still does not converge the random effect will be removed, if the model converges after removing the random center effects, the original model without random center effects will be re-assessed

The SAS procedure PROC MIXED will be used for analysis. Results will be presented with least squares mean (LSM) and standard error (SE) for treatment effects and LSM, SE, associated two-sided 95% confidence interval, and two-sided p-value for the treatment contrast.

In the analysis of laboratory data [REDACTED], the covariates FEV1 prior to inhalation and FEV1 15 to 30 min post inhalation will not be included in the MMRM.

- **Tipping point analysis for trough FEV1 at Week 12**

As a sensitivity analysis to evaluate the impact of missing data, a tipping point analysis will be performed for the primary endpoint trough FEV1 at Week 12. The delta-adjusting approach described in Ratitch et al (2013) will be used to find the tipping point, in a spectrum of conservative missing not at random (MNAR) assumptions, at which conclusions change from being favorable to QMF149 to being unfavorable. The basic idea is to impute the missing values using a regression based multiple imputation (MI) method based on the MAR assumption. The imputed Week 12 values for the QMF149 arms are then adjusted by a delta value.

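### Does the adolescent treatment effect at Week 12 need a named by-visit interaction term in the SAP?

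*SAP*

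**What the plan says.** SAP 2.2.1 plans adolescent results for the primary, key secondary and other secondary objectives. Where a table reports a fitted model, "the treatment effects in adolescent patients will be derived from the treatment x age subgroup interaction term by including all patients in the analysis". It then lists the subgroups for the primary endpoint, age group among them: "At week 12, the following subgroups will be used for supporting analyses of primary endpoint trough FEV1".

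The model being extended is the MMRM of SAP 2.5.2, with "visit (Days 2 and 85), and treatment-by-visit interaction as fixed effects". Its general form in SAP 6.6 begins "Dependent variable = intercept + treatment + age group + region + baseline value" and goes on to visit, treatment by visit and baseline by visit. The overall comparison is read "based on the treatment main effect and the coefficient for the treatment-by-visit interaction for Day 85 and treatment". For ACQ-7 the same model is used, and "ACQ-7 measurements are scheduled for Days -21, 1, 30 and 84".

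On the trough FEV1 subgroup models, SAP 2.5.4 says only that they are fitted "using the appropriate interaction term in the model and additional covariate as a fixed effect, if necessary"; protocol 9.4.5 says the same. SAP 2.2.1 leaves identification of the adolescent analyses to the table shells, and SAP 6.6 places the SAS code there. Those shells are not among the documents. SAP 1.1 puts the trial at about 750 patients, "including approximately 50 adolescent patients".

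**The concern.** The SAP lets the overall treatment effect differ by visit, since it carries a treatment-by-visit term and reads the contrast at Day 85. For adolescents it names a two-way term in the singular and nothing that varies with visit. Taken as the complete list of added terms, this fits one adolescent-minus-adult deviation to both visits. The result labelled Week 12 would then rest partly on the response one day after the first dose. For ACQ-7 the Week 12 result would rest partly on Day 30.

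If the deviation really changed between visits, the adolescent estimate would be biased and its confidence interval too narrow. The primary objective names adults and adolescents, and only about 25 adolescents per arm are expected, so readers may look closely at this figure. Two programmers could also fit different models and each believe they had followed the SAP. The same gap applies to the other subgroups analysed with the MMRM.

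**Working it through.** **Inputs from the documents.** 750 patients, 1:1, about 50 adolescents (SAP 1.1), so about 25 adolescents and 350 adults per arm. FEV1 SD 380 mL, difference 100 mL; ACQ-7 SD 0.80, difference 0.18; dropout 10% (SAP 3).

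**Assumed, because the documents do not give them.** The Day 2 SD and the correlation ρ between visits. The calculations leave out the baseline covariates and the random centre effect.

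**1. The plan's own figures.** With 338 completers per arm:
- Trough FEV1: SE = 380 × √(2/338) = 29.2 mL; 100/29.2 − 1.96 = 1.46; power 0.928 (stated 93%).
- ACQ-7: SE = 0.80 × √(2/338) = 0.0615; 0.18/0.0615 − 1.96 = 0.965; power 0.833. The product 0.928 × 0.833 = 0.773 (stated 77%).

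Both reproduce. Neither involves the subgroup model.

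**2. Share of Day 2 under a two-way term only.** For complete data, with f the adolescent fraction and s2, s85 the SDs at the two visits:

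weight = (1 − f) × (s85² − ρ·s2·s85) / (s2² + s85² − 2ρ·s2·s85), f = 50/750 = 0.067.

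- Equal SDs: the ratio is 0.5 for any ρ, so the weight is 0.933 × 0.5 = 0.467. With 10% missing at Day 85 it is about 0.50.
- s2/s85 = 0.8, ρ = 0.8: (1 − 0.64)/(0.64 + 1 − 1.28) = 1; weight 0.93.
- s2/s85 = 1.2 (Day 2 SD 456 mL), ρ = 0.8: (1 − 0.96)/(1.44 + 1 − 1.92) = 0.077; weight 0.07.

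Over SD ratios 0.8 to 1.2 and ρ from 0.3 to 0.8, complete data, the weight therefore runs from 0.07 to 0.93. In the narrower range of Day 2 SD 300 to 420 mL and ρ 0.5 to 0.7, with 0 to 10% missing, it is 0.31 to 0.82.

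**3. Precision.** With by-visit terms the adolescent estimate uses the adolescents' own Day 85 difference: SE = 380 × √(2/25) = 107.5 mL for complete data. The two-way estimate, with weight w, is w × (adolescent Day 2 − adult Day 2) + (1 − w) × adolescent Day 85 + w × adult Day 85. At equal SDs and ρ = 0.5 its variance is 380² × [0.08 × 0.751 + (2/350) × 0.218] = 380² × 0.0613, giving SE 94.1 mL. In the narrower range the SEs are 83 to 105 mL (two-way) against 108 to 112 mL (by-visit). The 95% half-widths are about 162 to 206 mL against 211 to 219 mL.

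**4. When pooling costs more than it saves.** The bias is the weight times the change in the adolescent deviation between visits. Mean squared errors are equal when that change is √(SE²by-visit − SE²two-way)/weight. At equal SDs and ρ = 0.5: √(107.5² − 94.1²)/0.467 = 52.0/0.467, or about 111 mL. Over the narrower range the break-even is 80 to 122 mL.

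**5. Size of the harm.** A 50 mL change gives a bias of 0.467 × 50 = 23 mL at equal SDs, against an SE of about 94 mL; coverage over the narrower range is 92.4 to 94.7%. A 100 mL change, as large as the whole planned treatment effect, gives a bias of 31 to 82 mL and coverage of about 84 to 94%. With no change there is no bias and the SE is correct.

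**6. ACQ-7.** With Day 30 SD assumed at 0.70 to 0.85 and ρ 0.5 to 0.7, the Day 30 weight is 0.37 to 0.69, with SE 0.19 to 0.22 (two-way) against 0.23 to 0.24 (by-visit).

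**7. The wording.** The sentence in SAP 2.2.1 governs all model-based adolescent tables. The 12-week diary ANCOVA, the Cox model and the negative binomial model have no visit factor, so one sentence covering them all would not name a visit term. Its purpose is to say that adolescent effects come from a model fitted to all patients, not from a fit to adolescents alone. The text specific to the trough FEV1 subgroups fixes Week 12 and asks for the appropriate interaction. In a two-visit model whose main contrast is read at Day 85, a by-visit interaction is a natural choice.

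**The case for a change.** The strongest case for a change is that the SAP is explicit about visits elsewhere. The primary contrast is tied to Day 85, and SAP 2.7.1 ties the Day 2 contrast to its own visit. Silence in the subgroup text is therefore conspicuous, and the one interaction actually named is two-way. The remedy is one sentence. Unless Day 2 is clearly more variable than Day 85, the borrowing is not small: with Day 2 no more variable than Day 85, the weight is at least 0.47 over the grid examined.

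The factual part stands: neither the SAP nor the protocol names a subgroup-by-visit term, and the arithmetic is right for the two-way model. What does not stand is the step from an unnamed term to a defect. The documents do not show that the two-way model will be fitted, and the detail is assigned to table shells that cannot be inspected. Nor is the two-way model plainly worse. It is unbiased and more precise if the deviation is constant, and the by-visit model does better on mean squared error only when the change between visits approaches the size of the planned effect. With half-widths above 160 mL under either model, about 50 adolescents cannot resolve a 100 mL effect. Stating the interaction terms and the visit of the contrast would be a courtesy to the programmer, but the plan is workable without it.

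**Conclusion.** No change to the plan is needed. The SAP leaves out a modelling detail that analysts following it would fill sensibly, by reading the adolescent contrast at Day 85 (Day 84 for ACQ-7). If they pooled visits instead, they would be making a defensible exchange of possible bias for precision. At equal SDs and complete data, 47% of the Week 12 adolescent estimate would come from Day 2; across the assumed covariances the share is 7 to 93%, so its size cannot be fixed from the documents. Pooling loses on mean squared error only if the adolescent deviation shifts by more than about 80 to 122 mL between visits.

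This rests on 25 adolescents per arm, a Day 85 SD of 380 mL, assumed Day 2 SDs and correlations, and a model without covariates or centre effects. SAP 2.5.4 labels the trough FEV1 subgroup analyses exploratory, and all the adolescent analyses lie outside the hierarchy of SAP 2.6.4. The primary and key secondary tests, their type I error and the stated 93% and 77% power are unaffected.
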